5.9 Safety Monitoring and Management

5.9.1 Infusion Safety Monitoring

On the day of ¹²⁴I-PEG-AVP0458 infusion, all patients will have baseline vital signs taken prior to the infusion. Saturated solution of Potassium Iodide (SSKI) (obtained from Hospital pharmacy), 10 drops twice daily, will be administered immediately prior to the infusion and will continue for a total of 10 days. All concomitant therapies and ongoing AEs occurring since the last visit will be reviewed and documented in the patient's medical history and eCRF.

For the infusion, vital signs and careful monitoring for symptoms such as allergic reactions will be measured and recorded during the infusion and the 4 hours post infusion completion. Vital signs and all AEs occurring during this period will be documented in the patient's medical history and eCRF.

All Grade 2 and higher AEs occurring during the infusion and up to 4 hours post-infusion are considered to be infusional toxicities regardless of relationship to drug and CTCAE v4.0 Grade.

5.9.2 Modifications for events occurring during or immediately after ¹²⁴I- PEG-AVP0458 infusion

There is a potential for the occurrence of allergic-type reactions during and immediately following the administration of ¹²⁴I-labelled PEG-AVP0458. If this occurs, the rate of infusion should be decreased or the infusion terminated completely in accordance with the following guidelines:

	Action ¹			
	Decrease rate of	Stop		
Clinical Manifestation	¹²⁴ I-PEG-AVP0458 Infusion by 50%	¹²⁴ I-PEG-AVP0458		
		Infusion ²		
↓ Systolic BP of 25-50 mmHg	X			
↓ Systolic BP of >50 mmHg		X		
Bronchospasm		X		
Severe shortness of breath		X		
Rigors	X			
Chills	X			

- 1 = Investigator discretion is necessary for a decision to reduce the rate or stop ¹²⁴I-PEG-AVP0458 infusion.
- 2 = The infusion may be re-initiated within 1 hour at the discretion of the Investigator. Should the clinical situation require that therapy be stopped again, the ¹²⁴I-PEG-AVP0458 infusion will not be restarted and the patient will be removed from study.

Management of Toxicities 5.9.3

Precautions for anaphylaxis must be available. Equipment for assisted ventilation and an established free flowing line must be available at the time of each infusion.

A life-threatening anaphylactic response of a sensitized human may appear within minutes after administration of a specific antigen and is manifested by respiratory distress often followed by vascular collapse or by shock without antecedent respiratory difficulty. Cutaneous manifestations are exemplified by pruritus and urticaria with or without angioedema and may be characteristic for systemic anaphylactic reactions. Gastrointestinal manifestations may include nausea, vomiting, crampy abdominal pain, and diarrhoea.

Diagnosis of anaphylaxis or choice of treatment and drug dosing is in the responsibility and at the discretion of the individual Investigator.

Appropriate supportive therapeutic interventions may be initiated at any time. Treatment with IV corticosteroids, antihistamines, pethidine, paracetamol, or adrenaline should be considered in the event of an allergic reaction or hypersensitivity. Refer to Appendix 2 for definition of allergic reaction or hypersensitivity according to CTCAE v4.0.

These events will be recorded in the patient's medical history and eCRF.

5.10 Criteria for Dose Escalation and Dose Selection

The Trial Management Committee is responsible for decisions regarding dose escalation (moving dose group 1 to group 2) and dose selection (moving from group 2 to 3), based on safety and dosimetry data.

For dose escalation, the decision is based on safety. If no patients in dose group 1 experience a DLT, then dose group 2 may commence 30 days after the last patient on the dose group 1 has received the PEG-AVP0458 infusion.

If any one patient in either cohort of 3 patients experiences a DLT, then 3 additional patients will be entered in that dose group. If additional patients are treated in the dose group 1, all patients entered must have been observed for 30 days before a new patient may receive an infusion in dose group 2. If greater than or equal to two DLTs are observed at a dose, then the MTD is considered to have been exceeded. If at most, one DLT is observed, the next 3 patients are assigned to the next highest dose. If two or more DLTs are observed, then the MTD is considered to have been exceeded.

In the event 2 or more patients experience DLT at the first dose level, an additional 3 patients will be entered at a 0.5mg/m² dose level

The Trial Management Committee will evaluate safety and dosimetry data available after the dose escalation part of the study (Interim Analysis) and determine the dose to be administered to the last 6 patients in the study.

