As this is a first in-human study, a single subject will receive the first dose of ¹²⁴I-PEG-AVP0458. Further dose administration will be sequential within each cohort to mitigate risks of anaphylactic or any other acute unexpected reactions. Administration of doses within a cohort will be staggered by 24 hours, i.e. there will be a period of 24 hours between the first, second and subsequent subjects in a cohort to observe and interpret reactions and adverse events. This time frame is sufficient to exclude any possible acute allergic or anaphylactic reactions to PEG-AVP0458.

After completion of accrual into the first cohort (1 mg/m 2 dose), the Trial Management Committee will review the safety data from these participants before a decision is made to escalate the dose to 10 mg/m 2 .

If no patients entered in the 1^{st} dose group experience a dose-limiting toxicity (DLT), and the Trial Management Committee agree, then the 2^{nd} dose group may commence on the higher dose of 10 mg/m^2 30 days after the last patient on the first dose group has received the 124 I-PEG-AVP0458 infusion. If any one patient in either cohort of 3 patients experiences a DLT, then 3 additional patients will be entered in that dose group. If additional patients are treated in the 1^{st} dose group, all patients entered must have been observed for 30 days before a new patient may receive an infusion in the 2^{nd} dose group. If greater than or equal to two DLTs are observed at a dose, then the MTD is considered to have been exceeded.

If at most, one DLT is observed, the next 3 patients are assigned to the next highest dose. If two or more DLTs are observed, then the MTD is considered to have been exceeded.

A DLT is defined as any of the following events occurring within 30 days of study drug administration:

- Any Grade 2 or greater allergic reaction.
- Any Grade 3 toxicity. Exceptions are: fever; asymptomatic hyperglycemia; hypophosphatemia; nausea, vomiting, or diarrhoea despite the use of optimal supportive medical therapy; leukopenia or thrombocytopenia that revert to baseline within three weeks of occurrence; lymphopenia without other dose-limiting events (eg opportunistic infection).
- Any Grade 4 toxicity.

The 30 days will allow identification and mitigation of the risks of any delayed immunogenic reaction before progressing to a subsequent cohort.

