In the event 2 or more patients experience DLT at the first dose level, an additional 3 patients will be entered at a 0.5mg/m² dose level.

After the last evaluation of the last patient enrolled in the second dose group (10 mg/m²), an interim analysis of the safety and dosimetry data will be undertaken. This analysis will be considered by the Trial Management Committee to ascertain which of the two doses, 1 or 10 mg/m², produces the better safety profile and dosimetry results for PEG-AVP0458. The dose selected will be based on imaging characteristics and pharmacokinetic data of ¹²⁴I-PEG-AVP0458 at each dose level. This chosen dose will be used to infuse the last 6 patients in the second part of the clinical study. This last group will enrol 3 patients with prostate cancer and 3 with ovarian cancer and will continue to evaluate safety as the primary endpoint.

Because of the low PEG-AVP0458 doses tested in this study, the fact that only two dose levels are being evaluated, and the past clinical experience with the intact parent antibody (CC49), this study is not expected to identify a maximum tolerated dose. It should be noted that the tracer dose of ¹²⁴I-labelled to PEG-AVP0458 has not been reported to be associated with adverse events in prior clinical trials of ¹²⁴I-labelled compounds.

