5.14 Criteria and rules for stopping patient treatment

An Investigator may stop a patient's participation for the following reasons:

- The patient withdraws consent.
- The patient is no longer able to participate.
- A patient can be withdrawn after discussion between the Sponsor and Investigator if eligibility criteria are violated or if the patient fails to comply with the protocol (e.g., nonadherence to study assessment visits).
- The Investigator's judgment that continued participation is no longer in the patient's interest.

Documentation of the details of withdrawal will be included in the eCRF. All patients who receive the ¹²⁴I-PEG-AVP0458 infusion will be evaluated for safety.

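### Two DLTs at a dose mean the MTD is exceeded, but if the second first occurs in group 3 no rule pauses dosing or calls the Trial Management Committee

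*Protocol*

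**What the plan says.** Section 5.10, repeated in 3.1, gives the criterion: "If greater than or equal to two DLTs are observed at a dose, then the MTD is considered to have been exceeded". The sentences around it deal with escalation. Expansion is written for the cohorts of three: "If any one patient in either cohort of 3 patients experiences a DLT, then 3 additional patients will be entered in that dose group". Progression follows: "If at most, one DLT is observed, the next 3 patients are assigned to the next highest dose". Two or more DLTs at the first dose level also lead to 3 patients at 0.5 mg/m² (protocol schema, 3.1 and 5.10).

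The Trial Management Committee decides on escalation from group 1 to group 2 and on "dose selection (moving from group 2 to 3), based on safety and dosimetry data". Its last described review is the interim analysis before group 3 (5.10, 8.4).

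On group 3, section 3.1 says: "This chosen dose will be used to infuse the last 6 patients in the second part of the clinical study". It adds that this group "will continue to evaluate safety as the primary endpoint". On timing, 3.1 says: "Administration of doses within a cohort will be staggered by 24 hours". DLTs are counted over 30 days. Section 5.14, on stopping, lists when an Investigator may end one patient's "participation for the following reasons".

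**The concern.** Group 3 adds 6 patients at a dose already given to 3 patients, or to 6 after expansion. A dose can enter group 3 with one DLT on record, or with none and then produce two. Either way the second DLT at that dose may first appear in group 3. The criterion then labels the dose as above the MTD, but the protocol does not say whether the next patient may be infused or who decides. Group 3 is half of a 12-patient first-in-human trial, or a third of an 18-patient one, and safety is still its primary endpoint.

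**Working it through.** **Does any section close the gap?**

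- Expansion (3.1, 5.10) covers the two cohorts of 3. Group 3 has 6 patients.
- The step to 0.5 mg/m² applies at the first dose level only. It adds patients at a lower dose; it is neither a hold nor a review.
- The committee's stated decisions (5.10, 8.4) end with the choice of the group 3 dose.
- Section 6.1 requires each DLT to be discussed with the Coordinating Principal Investigator, but names no action.
- Section 7 (alerts to the Principal Investigator), 7.2.2 (24-hour SAE reporting) and 10.2 (urgent-hazard amendment) give routes for a decision, but no trigger.
- Sections 5.9.2 and 5.14 concern one infusion or one patient.
- The 24-hour stagger sets timing. Six patients could be dosed over about 5 days, well inside the 30-day DLT window.

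**Sample size as stated.** 3 + 3 + 6 = 12 and 6 + 6 + 6 = 18, matching the 12-18 in section 3.2.

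**How often could it arise?** The protocol gives no DLT rate, so p = 0.05 and p = 0.10 are assumptions; q = 1 − p. Patients are treated as independent with the same p.

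A dose clears escalation in one of two ways:

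- 0/3: A = q³
- 1/3 then 0/3 (1/6 in total): B = 3pq² × q³

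The second DLT at the dose then first occurs in group 3 with probability:

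- after 0/3 (two needed among 6): 1 − q⁶ − 6pq⁵
- after 1/6 (one needed among 6): 1 − q⁶

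| | p = 0.05 | p = 0.10 |
|---|---|---|
| A | 0.857 | 0.729 |
| B | 0.116 | 0.177 |
| A + B | 0.973 | 0.906 |
| Share cleared at 1/6, B/(A + B) | 11.9% | 19.5% |
| Met in group 3 after 0/3 | 1 − 0.735 − 0.232 = 3.3% | 1 − 0.531 − 0.354 = 11.4% |
| Met in group 3 after 1/6 | 1 − 0.735 = 26.5% | 1 − 0.531 = 46.9% |
| Pooled, weighted by A and B | 6.0% | 18.4% |

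**How many infusions could a hold prevent?** If the criterion is met at group 3 patient k, 6 − k patients remain. The probability of meeting it at k is (k − 1)p²q^(k−2) after 0/3 and pq^(k−1) after 1/6. Summing (6 − k) times these:

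| Infusions prevented, upper bound | p = 0.05 | p = 0.10 |
|---|---|---|
| After 0/3 | 0.05 | 0.17 |
| After 1/6 | 0.70 | 1.31 |
| Pooled | 0.12 | 0.40 |

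These are upper bounds because they assume each outcome is known before the next infusion. In DLTs rather than infusions, the pooled saving is at most 0.05 × 0.12 = 0.006 and 0.10 × 0.40 = 0.04 per dose entering group 3.

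**The case against.** **Group 3 is not unprotected.** A reader might infer that no safety control reaches it, or that the protocol requires dosing above the MTD to continue. The documents support neither. DLT discussion, SAE reporting, the stagger and urgent amendments all apply, and a committee would not ordinarily keep giving a dose declared above the MTD. What stands is narrower: the text does not say so, and names no trigger or decision-maker.

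**An action is attached at 1 mg/m².** It would be too strong to say that nothing follows from two DLTs. If group 3 receives 1 mg/m², the step to 0.5 mg/m² could be read to apply. This is correct, but that step does not stop group 3 and has no counterpart at 10 mg/m².

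**The wording is fairly clear on counting.** The text names cohorts or dose groups when it means them, whereas the MTD sentence is framed by dose. Counting by dose is therefore the plain reading, although the escalation setting leaves some room for doubt.

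**The pooled figure is probably high.** It treats every cleared dose as equally likely to enter group 3. Sections 3.1 and 5.10 make safety part of dose selection, so a dose cleared at 1/6 is less likely to be chosen over one cleared at 0/3. The arithmetic is right, but the two routes should be read separately.

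**Two DLTs is a low bar for 9 or 12 patients.** It was written for 3 to 6 (2/6 = 33%), whereas 2/9 is 22% and 2/12 is 17%. As an automatic stop it would be poorly calibrated. As a trigger for committee review it is reasonable.

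**The expected benefit is small.** Section 3.1 anticipates little toxicity and does not expect to identify an MTD. This stands and limits the weight of the point.

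**Conclusion.** The gap is real and modest; closing it is a cheap improvement. The protocol has a per-dose criterion that can first be met in group 3, with no hold or committee review tied to it there. Whether to keep infusing patients is a protocol matter, not something to leave to an analysis plan.

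Under the assumed 5-10% DLT rates, the situation arises in about 3-11% of cases after clearance at 0/3 and 26-47% after clearance at 1/6. The pooled 6-18% is best taken as likely too high. These figures rest on the assumed rates, on independence between patients, and on counting by dose. They show how often the protocol would be silent, not how much harm would follow.

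**What to change.** State in sections 3.1 and 5.10 that DLTs are counted across all patients treated at a dose, including group 3. Add that a second DLT at that dose pauses further group 3 infusions until the Trial Management Committee has reviewed the data and decided whether to continue, lower the dose or stop. Word it as a review trigger, not an automatic stop, and add this decision to the committee's remit in 5.10 and 8.4.

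The cost is amendment wording and a possible pause in accrual, sometimes for a dose whose true DLT rate is low. With infusions as little as 24 hours apart and a 30-day DLT window, the pause protects mainly against acute DLTs. Those include the allergic reactions the stagger is meant to catch, which count as DLTs from Grade 2 if at least possibly related (3.1, 6.1). A delayed DLT may appear after all 6 patients have been dosed.

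### The escalation rule in Protocol 3.1 and 5.10 gives two instructions at 1 of 3 patients with a DLT, and counts DLT events in some sentences and patients in others

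*Protocol*

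**What the plan says.** Protocol 5.10 sets the rule for moving from 1 to 10 mg/m², and 3.1 repeats it almost word for word. If no patient in dose group 1 has a DLT, group 2 may start after 30 days. Then:

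- Expansion: "If any one patient in either cohort of 3 patients experiences a DLT, then 3 additional patients will be entered in that dose group".
- Waiting time after expansion: "If additional patients are treated in the dose group 1, all patients entered must have been observed for 30 days" before group 2 begins.
- MTD: "If greater than or equal to two DLTs are observed at a dose, then the MTD is considered to have been exceeded". A second sentence repeats this without tying it to a dose.
- Escalation: "If at most, one DLT is observed, the next 3 patients are assigned to the next highest dose".
- Step down: "In the event 2 or more patients experience DLT at the first dose level, an additional 3 patients will be entered" at 0.5 mg/m².

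Section 3.1 introduces the DLT definition with "A DLT is defined as any of the following events occurring within 30 days of study drug administration", so a DLT is an event. Section 6.1 adds that it must be at least possibly related to the study drug. Section 3.2 caps the escalation part at 12 patients. The schema bullets in the synopsis give the zero-DLT, expansion, 30-day and 0.5 mg/m² rules, but neither the at-most-one sentence nor the MTD sentences.

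**The concern.** There are two faults in the wording.

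**No denominator.** With exactly one DLT among the first three patients, the expansion sentence and the at-most-one sentence both apply. One keeps the next three patients at 1 mg/m²; the other sends them to 10 mg/m². Neither section says that the at-most-one sentence applies to six patients or only after expansion. It is also the only text that gives a criterion for escalating after expansion.

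**Two units.** One patient can have more than one DLT. If one of three has two, the MTD is exceeded by the event count, yet the patient-based rule still adds three patients at that dose.

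At stake is the safety rule for the single tenfold step of a first-in-human study. The Committee that applies it should have one instruction, in one unit.

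**Working it through.** **The plan's own figure.** Section 3.2 gives 12 to 18 patients. The minimum is 3 + 3 + 6 = 12. With both cohorts expanded it is 6 + 6 + 6 = 18. Both match, and 6 + 6 = 12 matches the stated maximum for the escalation part. These sizes fit a 3+3 with expansion at 1 of 3.

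**Scope of the escalation sentence.** Section 3.1 notes "the fact that only two dose levels are being evaluated". The sentence can therefore concern only the step from 1 to 10 mg/m².

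**Check 1: the missing denominator.** The protocol gives no DLT rate, so the true rate per patient, p, is an assumption; q = 1 − p.

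- 3+3 reading (escalate at 0 of 3, or at 1 of 3 followed by 0 of 3): q³ + 3pq² × q³
- Literal reading (escalate at 0 or 1 of the first 3): q³ + 3pq²
- Difference: 3pq² × (1 − q³)

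| Assumed p | P(1 of 3) = 3pq² | 1 − q³ | P(escalate), 3+3 | P(escalate), literal | Difference |
|---|---|---|---|---|---|
| 5% | 0.135 | 0.143 | 0.973 | 0.993 | 0.019 |
| 10% | 0.243 | 0.271 | 0.906 | 0.972 | 0.066 |
| 20% | 0.384 | 0.488 | 0.709 | 0.896 | 0.187 |
| 30% | 0.441 | 0.657 | 0.494 | 0.784 | 0.290 |

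For p = 10%: 3 × 0.10 × 0.81 = 0.243, and 0.243 × 0.271 = 0.066.

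**Check 2: events against patients.** Suppose one of the first three patients at 1 mg/m² has two drug-related DLTs.

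| Stage | Counting DLTs | Counting patients |
|---|---|---|
| First 3 patients | 2 DLTs: MTD exceeded | 1 of 3: add 3 at the same dose; 0.5 mg/m² not opened |
| After 3 more without a DLT | 2 DLTs: MTD exceeded, no escalation | 1 of 6: a 3+3 escalates; 0.5 mg/m² still not opened |

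At three patients neither count permits escalation. At six they give opposite decisions. If the event count is followed, 10 mg/m² is barred, while 0.5 mg/m² stays closed because it needs two affected patients. The text then gives no next dose.

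Let r be the share of DLT patients who have two or more DLTs, which is also an assumption. The six-patient case has probability r × 3pq² × q³.

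| Assumed p | 3pq² × q³ | r = 0.10 | r = 0.50 |
|---|---|---|---|
| 5% | 0.116 | 0.012 | 0.058 |
| 10% | 0.177 | 0.018 | 0.089 |
| 20% | 0.197 | 0.020 | 0.098 |
| 30% | 0.151 | 0.015 | 0.076 |

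**The case against.** The best defence is that the intended rule is not in real doubt. The at-most-one sentence comes after the expansion and 30-day rules, so read in order it describes the result after expansion. Direct escalation has its own zero-DLT sentence. If one DLT among the first three were enough, that condition, the mandatory expansion and the waiting rule for added patients would lose their purpose. The maximum of 12 also fits a 3+3. On units, two DLTs may be shorthand for two patients, and where the counts differ the event count is the stricter, so the mismatch cannot let through an escalation that the patient count forbids. There is oversight as well: "the Trial Management Committee will review the safety data from these participants before a decision is made to escalate the dose". Section 6.1 anticipates no severe adverse events, so the 20% and 30% rates, like any value of r, have no support in the protocol.

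Most of this stands, and it limits the practical risk. The low end of the assumed rates is the more relevant. But a clear intention does not remove conflicting instructions from a safety rule, and no other section settles whether DLTs or patients are counted. Committee review helps only if the Committee has one rule to apply.

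**Conclusion.** The concern holds; the rule should be corrected. As written it gives two instructions at 1 of 3, and no next dose at 1 of 6 patients with two or more DLTs at 1 mg/m². It is a contradiction in the wording; the underlying design is not in dispute.

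If the Committee applies the evident 3+3 and each affected patient has a single DLT, the effect is nil. The gain of 2 to 29 percentage points in the probability of escalating arises only if the sentence is applied literally to the first three patients, at assumed DLT rates of 5 to 30%. The 1.2 to 9.8% for the unit conflict rests further on the assumed 10 to 50% of DLT patients with more than one DLT. Both calculations treat patients as independent with a common DLT rate.

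**What to change.** In 3.1 and 5.10, and in the schema bullets to match, define the count as the number of patients with at least one DLT and state:

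- 0 of 3 at 1 mg/m²: escalate to 10 mg/m².
- 1 of 3 at either dose: add three patients at the same dose.
- At most 1 of 6 at 1 mg/m²: escalate to 10 mg/m².
- Two or more patients at a dose: MTD exceeded; if this occurs at 1 mg/m², open the 0.5 mg/m² cohort.

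Delete the duplicate MTD sentence.

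The cost is amendment wording only. The total remains 12 to 18 patients. The 0.5 mg/m² path uses 3 + 3 = 6 or 6 + 3 = 9 patients in the escalation part, within the stated maximum of 12.
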